On the other hand, research and medicine is moving away from behavioral responses to assess brain health (e.g. verbal responses, reaction time, etc.) and are moving toward more neuroimaging focused measures. Biological tests could enable us to detect pre-dementia and determine the prognosis of MCI subjects [16]. A promising biological test is EEG/ERP. Our group has previously shown group differences in ERPs for patients with MCI and CN [17, 18]. Other studies have reported promising ERP markers of pre-dementia [15,19, 20,] and progression of MCI to dementia [21]. However, ERP can be complex to process and labor-intensive, limiting its value in the clinical setting [22]. For example, the usual time for an ERP series measuring multiple cognitive domains typically lasts 1 hour, another 25 minutes for applying the EEG cap and ensuring all electrodes are connected, and some 30 minutes per paradigm (x2-3 paradigms).

The NeuroCatch™ Platform (NCP) offers key competitive advantages compared to other EEG platforms, having a rapid test time with automated processing, analysis and results display – benefitting patients and clinicians being significantly easier to use than current EEG systems, and it alleviates training and ramp up costs amongst EEG users. In this study, we will use the NPC to explore for ERPs that could predict progression to dementia in patients with MCI. The present study will make an initial assessment of the capacity of the NCP to detect cognitive decline and predict conversion to dementia in patients with MCI.

Hypotheses:

In Cognigram, we hypothesize that the following will occur:

- i. Significant differences in the CG scores at baseline will be found between MCI and CN groups
- ii. MCI subjects will show greater longitudinal changes than the CN subjects
- iii. Intra-individual Significant longitudinal changes in the CG performances at 3 and/or 6 months and/or 9 months and/or 12 months, will relate to the prospective clinical outcome at 12-months, and/or 24-months, and/or 36-months.
- iv. The CG will show a higher sensitivity in detecting cognitive changes, and a higher predictive power of longitudinal clinical outcome than the pencil-and-paper MoCA test.

In NeuroCatch, we hypothesize that the following will occur:

- I. Significant differences in the ERP parameters (amplitude and latency of ERPs such as N100, N400, P300) at baseline will be found between MCI and CN groups

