- II. MCI subjects will show greater longitudinal changes in ERP parameters than the CN subjects
- III. Intra-individual significant longitudinal changes in ERP parameters at 6 months and/or 12 months and/or 24 months, will relate to the prospective clinical outcome at 12-months, and/or 24-months, and/or 36-months.
- IV. The NCP will show a higher sensitivity in detecting cognitive changes, and a higher predictive power of longitudinal clinical outcome than the pencil-and-paper MoCA test.

b) Objectives of the project:

The objectives of the project are as follows:

- i. To discriminate CG longitudinal changes related to neural damage from normal variations in cognitively normal (CN) older adults
- ii. To determine if CG baseline score is related to the clinical outcome at 12-months, 24-months, and 36-months
- iii. To determine if intra-individual CG changes at 3, 6, 9, and 12 months, are related to the clinical outcome at 12-months, 24-months, and 36-months.
- iv. To compare the powers of CG and MoCA for predicting longitudinal clinical outcomes.
- v. To discriminate ERP longitudinal changes (e.g., changes in N100, N400, P300 amplitudes and latencies) related to neural damage from normal variations in cognitively normal (CN) older adults.
- vi. To determine if ERP baseline parameters (e.g. amplitude of N100, N400, P300) is related to the clinical outcome at 12-months, 24-months, and 36-months
- vii. To determine if intra-individual changes in ERP parameters at 6, 12, and 24 months, are related to the clinical outcome at 12-months, 24-months, and 36-months.
- viii. To compare the powers of NCP and MoCA for predicting longitudinal clinical outcomes.

c) Clinical relevance of the project:

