 2. **Montreal Cognitive Assessment test (MoCA):** is a validated, rapid screening instrument for mild cognitive dysfunction. It assesses different cognitive domains: attention and concentration, executive functions, memory, language, visuoconstruction, conceptual thinking, calculations and orientation. Time to administer is approximately 10 minutes. The total possible score is 30 points: a score of 26 or above is considered normal (**Appendix 2: MoCA**).
 3. **Functional Activities Questionnaire (FAQ):** is a brief questionnaire developed by Pfeffer et al. [9], which asks an informant to rate the patient's ability to perform instrumental activities of daily living. Patient's ability can be rated from normal to dependent. Time to administer is approximately 5-10 minutes (**Appendix 4: FAQ**).
 4. **General Practitioner assessment of Cognition tool (GPCOG):** is a screening tool for cognitive impairment. It has been designed for general practitioners, primary care physicians, and family doctors. It includes a testing part for the patient, and an interview part for the informant. In this study, only the interview section of the GPCOG will be administered to both the participant and the Study Partner. A specific question of the original interview was deleted ("*Does he/she need more assistance with transport?*") since it is already assessed in the FAQ, and replaced by ("*Does he/she repeat the same statement or question within a conversation, not remembering it was just said?*"), which is a common complaint in dementia. Lastly, a scale for rating the perceived impact of the cognitive difficulties in daily life functions was included (**Appendix 5: GPCOG**).

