- c) Cognitive decline inside the MCI spectrum (for MCI subjects)
- d) Conversion to dementia

b) Primary Outcome Measures:

- Baseline CG scores (accuracy and reaction speed)
- Baseline MoCA scores
- Baseline ERP's amplitudes and latencies (e.g. N100, N400, P300) means and standard deviations.
- Longitudinal changes in CG scores
- Longitudinal changes in MoCA scores
- Longitudinal changes in ERP's amplitudes and latencies
- Neuropsychological battery scores (at baseline and follow-up)
- FAQ and GPCOG scores (at baseline and follow-up)
- Clinical outcomes: stable normal cognition, reversion to normal cognition, conversion to MCI stable MCI, cognitive decline inside the MCI spectrum, conversion to dementia.

c) Plan for the Analyses of the Results:

Baseline CG, MoCA scores, and ERP components (mean amplitude +/- standard deviation of N100, N400, P300 and others) will be correlated with the NPS battery, GPCOG and FAQ's score. Longitudinal within-subject and within-group differences in the CG, MoCA, and ERP components will be correlated with longitudinal within-subjects and within-group changes in the NPS battery, GPCOG and FAQ's scores. Regression analysis will also be performed at follow-up, to explore the CG, ERP, and MoCA's predictive capacities for cognitive and functional declines. Additionally, Receiver's Operative Characteristics curves will be performed for assessing the CG, ERP, and MoCA's discriminative powers for detecting longitudinal clinical outcomes, and discriminating CN/MCI/dementia cross-sectionally. Positive predictive and negative predictive values of CG, MoCA, and ERPs will be explored.

13. SAMPLE SIZE AND RESEARCH SITES (See Guidelines)

- a) Total number of research participants being recruited at all centers globally: **CG: 60 (30 MCI, 30 CN); NCP: 60 (30 MCI, 30 CN).**
- b) Total number of sites: **1** and list countries: **1**
- c) Please indicate the number of research participants to be recruited at each COREB research site below:

University of Ottawa – Social Sciences and Humanities	
University of Ottawa – Health Sciences and Sciences	

University of Ottawa – Heart Institute	
Ottawa Hospital	
Children’s Hospital of Eastern Ontario	
Montfort Hospital	
The Rehabilitation Centre	
Bruyère Continuing Care	X
Royal Ottawa Health Care Group	
Other (Specify)	

d) Is the enrollment of individuals into multiple studies likely to be an issue in this subject population?

Yes No

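### Hypotheses iv and IV claim that CG and NCP outperform MoCA, but section 12c estimates no difference from MoCA, ignores the pairing and leaves the CG and ERP scores to be compared open

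*Protocol*

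**What the plan says.** Section 11a of the Protocol makes two directional claims. Hypothesis iv: "The CG will show a higher sensitivity in detecting cognitive changes". Hypothesis IV: "The NCP will show a higher sensitivity in detecting cognitive changes". Each goes on to claim "a higher predictive power of longitudinal clinical outcome than the pencil-and-paper MoCA test". Section 11b repeats the contrast as objective iv, "To compare the powers of CG and MoCA for predicting longitudinal clinical outcomes", and objective viii, "To compare the powers of NCP and MoCA for predicting longitudinal clinical outcomes". The section 10 summary also says the predictive capacities of the tools are to be compared.

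Section 12c lists four kinds of analysis:
- correlation of CG, MoCA and ERP values with the neuropsychological battery, GPCOG and FAQ;
- regression to explore predictive capacity;
- ROC analysis, where Receiver's "Operative Characteristics curves will be performed for assessing the CG, ERP" and MoCA, both for longitudinal clinical outcomes and for cross-sectional discrimination;
- exploration of positive and negative predictive values.

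Section 12b lists CG accuracy and reaction speed, ERP amplitudes and latencies (N100, N400 and P300 as examples) and MoCA scores, each at baseline and as longitudinal change. Section 12c leaves the ERP component list open-ended.

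**The concern.** A claim that one test predicts better than another is a claim about a difference. Here both tests are taken by the same person at the same visit, so the difference should be estimated within participants. Every analysis in 12c stops at how well each tool does alone. Followed as written, it leaves superiority to be read off two point estimates, with no interval for their difference.

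The candidates are also unequal in number. MoCA gives one total per visit, while CG gives several scores and ERP at least six, and none is designated for the comparison. With few converters, the highest of several chance AUCs sits well above 0.50. An unplanned choice among scores could therefore make a tool look better than MoCA when it is not.

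**Working it through.** **1. The plan's own figure.** Section 13f takes 30 MCI as allowing for up to 50% attrition against published samples of 15-20. 15/(1 - 0.5) = 30, so it reproduces. The cited effects are d = 1.03 (CG decline over 12 months) and 0.46 (ERP, MCI against controls). Neither is a contrast with MoCA, so the Protocol contains no figure for iv or IV.

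**2. Inputs.**
- From the Protocol: 30 MCI and 30 CN per study (13a); three named ERP components x two parameters = 6 scores (12b); four CG tasks (12a), so 4 x 2 = 8 scores if accuracy and speed are both used for each task (assumption); one MoCA total per visit.
- Assumed, because the Protocol gives none: 9 converters among the 30 MCI, MoCA true AUC of 0.60 to 0.80, correlation between scores of 0 or 0.5.

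**3. Chance that the best useless score beats MoCA.** The method is Monte Carlo with normal scores. MoCA is shifted in converters by sqrt(2) x the normal quantile of its true AUC, and the k other scores are pure noise. Empirical AUC = [R - m(m+1)/2] / [m(n - m)], where R is the rank sum of the m converters among n. The table gives the share of studies in which the largest of the k AUCs exceeds MoCA's, with direction fixed in advance. Ranges run from correlation 0.5 to 0.

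| MoCA true AUC | One prespecified score | Best of 6 | Best of 8 |
|---|---|---|---|
| 0.60 | about 27% | 51-63% | 54-68% |
| 0.70 | about 10% | 26-33% | 28-37% |
| 0.80 | about 2% | 7-9% | 8-11% |

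Repeat runs agree to within about one percentage point. Further results:
- The mean best AUC of six useless scores with 9 converters is 0.61-0.65, not 0.50.
- At MoCA 0.70, best of 6 rises to 41-46% if each score's direction is also chosen from the data.
- At MoCA 0.70, direction fixed, best of 6 is 34-43% with 5 converters and 21-28% with 15.
- Cross-sectionally (30 v 30), best of 6 is about 7-11% at MoCA 0.70 and under 1% at 0.80.

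**4. Precision of the paired difference.** Hanley-McNeil at AUC A = 0.75 with 9 and 21: Q1 = A/(2 - A) = 0.600; Q2 = 2A²/(1 + A) = 0.643; A² = 0.5625.

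Variance = [0.1875 + 8(0.600 - 0.5625) + 20(0.643 - 0.5625)]/(9 x 21) = about 2.095/189 = 0.0111, so SE = 0.105.

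Paired SE = 0.105 x sqrt(2(1 - r)), which is 0.105 at r = 0.5 and 0.125 at r = 0.3. The half-width is 1.96 x SE = 0.21 to 0.24.

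**5. Behaviour of a paired test.** Simulated DeLong test, one-sided 0.025, correlation 0.3:
- One prespecified score: false superiority about 2.4-3.3% when the true AUCs are equal, and at most 0.1% for a useless score against MoCA 0.70.
- All 6 or 8 scores tested without correction: 11-15% when the AUCs are equal.
- Power for 0.85 against 0.70 with 9 converters: about 26%.

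**The case against.** **The SAP is not shown.** It may supply a paired test, and nothing in 12c forbids one. The choice between DeLong and bootstrap does belong there. But 12c names its methods, and those methods do not answer two of the Protocol's own hypotheses. That mismatch is within the document.

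**The aims are modest.** Section 11a speaks of an initial assessment and 12c of exploring. This has force, and it is why exploratory wording is an acceptable remedy. As they stand, iv and IV are worded as superiority claims.

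**Stronger readings that the Protocol does not support.**
- A reader might infer that the best CG or ERP score will be picked and set against MoCA. The text leaves room for that but does not say so, and the percentages above depend on it.
- A reader might infer a contest between a fixed MoCA threshold and optimised thresholds for the new tools. The statement that "a score of 26 or above is considered normal" describes the instrument under Material. 12c does not make it an analysis threshold, a ROC curve needs none, and no data-driven cut-offs are announced.
- A reader might take ROC curves to be the only planned analysis. They are not, although the other analyses do not compare tools either.
- A reader might say that a useless tool wins about half the time. That depends mainly on MoCA's true AUC and on choosing direction from the data. MoCA also has baseline and change scores, so counting both for ERP but only one for MoCA would be unfair.

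**Conclusion.** The concern holds as a mismatch between claim and analysis. Two superiority hypotheses and two comparative objectives have no estimate of a difference behind them in 12c, no use of the paired design and no named score for either new tool.

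The risk of apparent superiority from a useless tool is conditional on choosing the best score. It is substantial for prediction in 30 MCI when MoCA is weak to moderate, and small when MoCA is good or the comparison is cross-sectional. The number of converters, MoCA's AUC and the correlations are assumptions, so only the range should be quoted. The absence of a difference estimate does not depend on any of them.

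**What to change.** In section 12c:
- Name one CG score and one ERP score for the comparison, with the clinical outcome and time point.
- Set each against the corresponding MoCA score: baseline against baseline, change against change.
- Report the paired AUC difference from MoCA with its 95% interval (DeLong or bootstrap) in the same participants.
- Label all other CG and ERP scores exploratory.
- Claim superiority only if the interval excludes zero. Otherwise, word hypotheses iv and IV as exploratory.
- State the expected half-width of about 0.21-0.24, with its assumptions (9 of 30 converting, AUC 0.75, correlation 0.5 to 0.3).

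The cost is plan wording, with no new data or visits. The investigators must nominate one score per tool in advance and accept that superiority may stay unproven.

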Appendix 1 - List of Investigators and Institutions

Application No. 281621

Date: 29 May 2018

Investigators; Names and addresses of Institutions
[name], Principal Investigator Elisabeth Bruyère Hospital [name]

10. STUDY SUMMARY/ABSTRACT (See Guidelines)

This summary must be suitable for lay audience (approximately 200 words). Please note that this is not a substitute for the full protocol, and do not refer the reader to sections of an attached protocol.

This research project will test two new computerized technologies in the detection of brain changes related to Mild Cognitive Impairment (MCI) and dementia due to Alzheimer's disease. These technologies are:

1) Computerized cognitive battery: Cognigram (CG) (*Appendix 1: Cognigram*)

Computerized assessments have multiple advantages for the early detection of subtle changes in cognition in older adults. One of their main advantages is their higher precision when measuring accuracy and speed of responses, compared to pencil-and-paper tests. They also allow a greater reliability in measures, as tests are given in a standardized format without the interference of an evaluator [1]. Finally, by including automatized instructions and reports, they are suitable for off-site or long-distance use.

The present study aims to validate the Cognigram™ (CG) [2] computerized cognitive tool (*Appendix 1: Cognigram*), in a prospective and longitudinal fashion, determining if changes in the CG scores over 3, 6, 9, and 12 months, can predict progression to dementia at 1-year, 2-years, and 3-years, for patients with Mild Cognitive Impairment (MCI).

For the purpose of this project, a total sample of 30 MCI and their study partners, and 30 cognitively normal subjects (CN), will be recruited. Study partners of MCI subjects will answer the functional questionnaire and the cognitive questionnaire required for defining the clinical status of participants. It is mandatory for MCI participants to have a study partner available in order to participate in this study.

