The participants will undergo CG and Montreal Cognitive Assessment (MoCA) (*Appendix 2: MoCA*) testing sessions at baseline, 3-months, 6-months, 9-months, and 12-months. The capacities for predicting clinical longitudinal outcomes (i.e., reversion to normal cognition, significant decline within MCI spectrum, or progression to dementia) of CG and MoCA will be compared. The clinical outcome will be assessed using a Neuropsychological battery, a functional assessment and a brief cognitive questionnaire at baseline, 12-months, 24-months and 36-months. It is expected that changes in CG scores will be sensitive to cognitive decline, allowing an early prediction of progression of the cognitive impairment.

2) The NeuroCatch™ Platform (NCP) (*Appendix 14: NCP*)

Event-related potentials (ERP) are non-invasive, low-cost, electrophysiological methods that allow recording of the electrical activity of the brain *in vivo* through an Electroencephalogram (EGG). They are free from cultural and educational influence and can provide insights into the cognitive processes (Jiang et al., 2015). ERP could enable us to detect brain changes and determine the prognosis of MCI subjects [16].

The NCP (*Appendix 14: NCP*), an investigational medical device system developed by NeuroCatch Inc., consists of an EEG software and hardware that captures brain health information. It offers a quick (i.e., 10 minutes for EEG preparation and 6 minutes for each task of EEG recording), simple (i.e., includes only 8 electrodes), and easy-to-use solution (i.e., includes a computerized software that automatically analyzes data and outputs graphs in less than 1 minute) for the acquisition of EEG and ERP.

For the purpose of this project, a total sample of 30 MCI and their study partners, and 30 cognitively normal (CN) subjects will be recruited. The participants will undergo NCP (*Appendix 14: NCP*) and MoCA (*Appendix 2: MoCA*) testing sessions at baseline, 6-months, 12-months, 24-months, and 36-months. The capacities for predicting clinical outcomes (i.e., reversion to normal cognition, significant decline within MCI spectrum, or progression to dementia) of the NCP and MoCA tests will be

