 5. **Neuropsychological battery (NPS):** a Neuropsychological battery assessing episodic memory, executive functions and attention, language, and praxis will be administered for defining the clinical outcome at baseline, 1 year, 2-years, and 3-years. The RA will administer the battery, in a private office at BRI. Scores will be registered using Study ID, with no personal identifiers. The specific tests administered will be the following: Mini-mental state examination (MMSE), Hopkins Verbal Learning test, Rey-Osterrieth Complex Figure test (copy, immediate and delayed recall), Stroop Effect test, the Digit-symbol coding and symbol search subtests of the Wechsler Adult Intelligence Scale, Trail Making Tests A and B, and the Semantic Verbal Fluency test (animals). The total administration time is expected to be 50-60 minutes, depending on the participant's speed. Participants will be given a 10 minutes break in-between

the neuropsychological testing. The Neuropsychological testing will be performed by the RA n°2, which is a trained psychologist with experience in Neuropsychological assessments.

B) When choosing to participate in the NCP study only:

	Visit 1 (baseline)	Visit 2 (6 months)	Visit 3 (12 months)	Visit 3 (24 months)	Visit 4 (36 months)
Tests	1. MoCA (10') 2. NCP (25') 5' break 3. NPS battery (60') with a 10' break in-between 4. Questionnaires (5')	1. MoCA (10') 2. NCP (25') 3. Questionnaires (5')	1. MoCA (10') 2. NCP (25') 5' break 3. NPS battery (60') with a 10' break in-between 4. Questionnaires (5')	1. MoCA (10') 2. NCP (25') 5' break 3. NPS battery (60') with a 10' break in-between 4. Questionnaires (5')	1. MoCA (10') 2. NCP (25') 5' break 3. NPS battery (60') with a 10' break in-between 4. Questionnaires (5')
Time (approx.)	100 minutes (115 with breaks)	40 minutes	100 minutes (115 with breaks)	100 minutes (115 with breaks)	100 minutes (115 with breaks)

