Effect sizes are also going to be computed in our studies as standardized mean differences, expressed as the product of the difference in means of both groups (or both times, in intraindividual analyses) divided by their pooled standard deviation. An effect size is a robust measure of study variability as each study is given a standardized weight corresponding to their sample size, which may be used for future power analyses [21].

14. DESCRIPTION OF STUDY POPULATION (See Guidelines)

a) Inclusion criteria - Who is being recruited and what are the criteria for their selection?

The following inclusion criteria will be considered:

- Age \geq 60
- Capable of giving consent, as stated by the University of California, San Diego Brief Assessment of Capacity to Consent (**Appendix 9: UBACC**)
- Meeting the diagnostic criteria of MCI or CN (described below)
- **For MCI subjects: availability of a Study partner, defined as a person that knows the participant for at least 5 years, has frequent contact with them (\geq 2 days/week) and is knowledgeable of their functioning in activities of daily living

b) Exclusion criteria – Which research participants are excluded from participation?

The following exclusion criteria will be considered

- Significant visual, hearing, or hand-motor impairment that may interfere with the CG testing sessions or Neuropsychological Assessment
- Currently participating in Clinical Drug Trials
- Currently participating in multiple observational studies (\geq 2)
- Meeting the DSM-IV criteria for dementia at baseline
- Color blindness
- No consent to UBACC administration in MCI subjects
- Non-fluent in English
- Active Major depression, Stroke, Traumatic Brain Injury, substance abuse, any other neurological disease (with the exception of MCI in the MCI group).
- **For NCP project only:**
 - In-ear hearing aid or cochlear implant, hearing device
 - Implanted pacemaker
 - Metal or plastic implants in skull
 - History of seizures
 - Allergy to rubbing alcohol or EEG gel
 - Unhealthy scalp (apparent open wounds and/or bruised or weakened skin)

c) Diagnostic criteria:

Mild Cognitive Impairment (MCI):

Diagnosis of MCI in recruitment database and corroborated at baseline by:

- 1) Objective cognitive impairment: expressed as \geq 1.5 SD below the normative mean in at least one test of the NPS tests, AND
- 2) MMSE $>$ 19, AND
- 3) Subjective Cognitive Impairment, expressed by participant and/or study partner: defined by GPCOG, AND

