- 4) Absence of significant functional impairment: score \leq 5 in the FAQ.

Cognitively Normal (CN):

Diagnosis of CN in recruitment database –or absence of diagnosis of MCI or dementia- and corroborated at baseline by:

- 1) Normal score expressed as within 1 SD from the normative mean in every test of the NPS tests, AND
- 2) MMSE \geq 27

** Results and associated data relating to testing for eligibility/inclusion will be destroyed for those persons found to be ineligible and not enrolled.

c) Which linguistic groups will be recruited?

French-speaking: **English-speaking:** Other (specify):

Please note that all documentation (e.g. advertisements, telephone scripts, information/consent forms, de-briefing summaries, etc) should be translated into the language of each linguistic group being recruited for the study and submitted for review after the primary version (English or French) is approved.

15. IDENTIFICATION AND RECRUITMENT OF RESEARCH PARTICIPANTS (See Guidelines)

a) Describe how the research study will be publicized for recruitment purposes. If the initial contact is by letter, telephone, e-mail, web-site and/or advertisement, attach applicable copies of the text to be used. For studies recruiting participants from different linguistic groups, please forward the translated texts after the primary versions (English or French) texts have been approved.

Not applicable. The study will not be publicized.

Texts are attached: Yes No Not applicable

Translated texts will follow: Yes No Not applicable

b) If the identification of prospective subjects will involve using information from their personal health information record, describe how the patient's agreement to be contacted by the researcher(s) will be obtained by members of his/her health care team or by the custodian of his/her health information record.

Not applicable

c) Once identified, how will prospective research participants be recruited?

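### The cognitively normal (CN) entry rule gives no direction for its 1 SD limit, and a CN subject who declines has no informant functional data with which to confirm MCI or separate it from dementia

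*Protocol*

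**What the plan says.** **Entry rules (section 14c, Diagnostic criteria).** CN subjects need a "Normal score expressed as within 1 SD from the normative mean in every test of the NPS tests", together with an MMSE of at least 27. MCI criterion 1 asks for a result at least "1.5 SD below the normative mean in at least one test of the NPS tests". MCI criteria 2 to 4, all joined by AND, are an MMSE above 19, "Subjective Cognitive Impairment, expressed by participant and/or study partner: defined by GPCOG", and "Absence of significant functional impairment: score" of 5 or less on the FAQ. A note under the criteria adds: "Results and associated data relating to testing for eligibility/inclusion will be destroyed for those persons found to be ineligible and not enrolled".

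**Battery (section 12a, Material).** "The specific tests administered will be the following: Mini-mental state examination (MMSE), Hopkins Verbal Learning test", followed by the Rey figure (copy, immediate and delayed recall), Stroop, digit-symbol coding, symbol search, Trail Making A and B, and semantic fluency. The MMSE is therefore part of the battery that the CN rule refers to.

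**Function and follow-up status.** The FAQ is completed by an informant (section 12a, Material). Sections 12a and 14a require a study partner for MCI subjects only. The summary in section 10 says "Study partners of MCI subjects will answer the functional questionnaire and the cognitive questionnaire required for defining the clinical status of participants", and also "The clinical outcome will be assessed using a Neuropsychological battery, a functional assessment and a brief cognitive questionnaire". In all three visit designs in section 12a (CG only, NCP only, both), the FAQ goes to study partners of MCI subjects, at baseline and at follow-up. CN subjects have the neuropsychological battery and the participant form of the GPCOG, which carries an added daily-impact scale. A blinded panel of two physicians and two psychologists assigns status at 12, 24 and 36 months. Its categories include conversion to MCI for CN subjects and conversion to dementia with no group restriction. Both also stand among the primary outcome measures in section 12b.

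**The concern.** The CN group supplies the normal variation against which objectives i and v in section 11b judge change. A rule that can be read two ways can recruit two different groups. One is bounded only from below. The other is a narrow middle band that turns away people for doing well on a single test. Because screening results of ineligible persons are destroyed, nobody could later find out which reading was applied or reverse it.

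The second matter is what a CN conversion means. Section 12a treats functional impairment as central to diagnosing dementia and gives that as the reason for having an informant. CN subjects are not required to have one. If a CN subject's test scores fall, the panel lacks the item that the MCI definition uses to rule out significant functional impairment. A CN conversion therefore rests on a different reference standard from an MCI subject's outcome, and the protocol does not say so. The label has consequences: it starts six-monthly consent-capacity assessment (section 16h) and advice to notify the family doctor (section 18k).

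**Working it through.** The protocol states no figure that depends on either rule, so there is none to reproduce.

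**(a) Size of the difference between the two readings**

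Inputs:
- The number of scores, k, counted from the battery in section 12a. Leaving out the MMSE, which has its own criterion, there are 8 tests. There are 10 scores if Rey copy, immediate and delayed recall count separately.
- Not in the protocol, and assumed: scores are normal with equal inter-test correlation r between 0.3 and 0.6, and candidates resemble the normative population.

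One-factor model, with z the common factor, Phi the normal distribution function and E the mean over z:
- literal rule: P = E[ (Phi((1 - sqrt(r) z)/sqrt(1 - r)) - Phi((-1 - sqrt(r) z)/sqrt(1 - r)))^k ]
- lower bound only: P = E[ (1 - Phi((-1 - sqrt(r) z)/sqrt(1 - r)))^k ]
- rejected only for a high score, among those with no score below -1 SD: 1 - literal/lower bound

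| k | r | Literal | Lower bound only | Rejected only for a high score |
|---|---|---|---|---|
| 8 | 0.3 | 6.9% | 40.6% | 83.1% |
| 8 | 0.6 | 15.4% | 54.8% | 71.9% |
| 10 | 0.3 | 3.8% | 35.3% | 89.4% |
| 10 | 0.6 | 11.0% | 51.5% | 78.6% |

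At r = 0.7 with k = 8 the literal pass rate is 21.6% against 59.8%, and 63.9% of those with no low score are still rejected.

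The lower-bound rule shifts the CN group upwards. The mean factor score of those who pass runs from 0.65 (k = 8, r = 0.6) to 0.80 (k = 10, r = 0.3). On a measure that correlates 0.3 with the common factor, the shift is 0.3 x 0.65 = 0.19 to 0.3 x 0.80 = 0.24 SD. At a correlation of 0.5 it is 0.32 to 0.40 SD. The literal rule gives a shift of 0.00.

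**(b) What a CN subject can supply against the MCI definition**

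| MCI criterion (section 14c) | Available for a CN subject at follow-up? |
|---|---|
| 1. Low neuropsychological score | Yes, at 12, 24 and 36 months |
| 2. MMSE | Yes, within the battery |
| 3. Subjective complaint (GPCOG) | Yes; the participant's own report suffices |
| 4. FAQ | No; no informant is named in any of the three designs |

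Three of four criteria can be scored. The GPCOG impact scale gives some self-rated functional information, but section 12a states no cut-off or role for it. The CN definition needs only the battery and the MMSE, so a finding of stable normal cognition does not call on the FAQ. The missing item matters only once a CN subject declines.

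**The case against.** **On the entry rule.** The context points to a lower bound. The criterion speaks of a normal score, it is the counterpart of an impairment rule that looks downwards, and its companion MMSE rule is a floor only. That stands, and a reader should not infer that the site applies or intends the two-sided rule; nothing shows that it does. What remains is an eligibility rule whose words do not settle the matter. The pass rates rest on an assumed correlation and a normative population. Candidates already labelled normal by a memory clinic may pass more often.

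**On conversion.** The MCI definition is worded for baseline and opens with a database diagnosis that a CN converter would not have. Follow-up status is a panel judgement, and nothing obliges the panel to apply the four entry criteria. So the stronger reading, that conversion to MCI cannot be established in CN subjects at all, does not hold. Nor should a reader count all CN follow-up assessments (30 x 3 = 90 of 60 x 3 = 180 per study) as compromised, because stable normal cognition needs no FAQ.

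It is also tempting to see a flat contradiction with section 15e, which says all participants have identical testing, and with the functional assessment mentioned in section 10. Both are weak evidence. Section 15e explains why there is no experimental control group, and an informant questionnaire is not testing of the participant. Section 10 itself assigns the functional questionnaire to partners of MCI subjects.

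Finally, the main objective concerns MCI subjects, and no hypothesis is specific to CN conversion. That limits the weight of the point but does not close the gap for a listed outcome.

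**Conclusion.** Both parts hold in a limited form, and both should be corrected.

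(a) The CN rule leaves its direction unstated. A lower bound was probably intended. If the rule were applied literally, about 4-15% of a normative population would pass, against 35-55% under a lower bound, and 72-89% of people with no low score would be turned away for a high one. These figures assume 8 to 10 equally correlated normal scores with r of 0.3 to 0.6, so they illustrate the difference and do not forecast recruitment.

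(b) For a CN subject who declines, the panel lacks the functional criterion of the only MCI definition in the protocol and has no informant data to separate MCI from dementia. It can still assign a status by judgement. The gap is confined to CN decliners, whose number the protocol does not allow one to estimate. It is a weakness in what a CN conversion can be said to mean and does not invalidate the outcome classification as a whole.

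**What to change.** **(a)** In section 14c, reword CN criterion 1 to require that no neuropsychological score lies more than 1 SD below the normative mean. Acknowledge that the CN group will then sit somewhat above the norm: about 0.19 to 0.24 SD on a measure correlating 0.3 with general ability, and 0.32 to 0.40 SD at 0.5, under the same assumptions.

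**(b)** Reconcile sections 10, 12a, 12b, 14c and 15e so that CN follow-up status is stated to rest on what CN subjects supply: the battery including the MMSE, and the participant GPCOG with its impact scale, whose role should be given. Report the result as cognitive conversion, make no claim of dementia conversion in CN subjects without functional data, and say that CN and MCI outcomes rest on different reference standards.

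**Cost.** Amendment wording only, with no new test, visit or staff. The price is that CN and MCI outcomes are not fully comparable. Naming an informant for CN subjects would also close the gap, but it adds a person and a questionnaire that the present design does not require.
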